### **6.6.2 Exclusion Criteria**

- EC 1 In the opinion of the Investigator, any known contraindications to an AF ablation, TEE, or anticoagulation
- EC 2 Any duration of continuous AF lasting longer than 12 months
- EC 3 History of previous left atrial ablation or surgical treatment for AF/AFL/AT
- EC 4 Atrial fibrillation secondary to electrolyte imbalance, thyroid disease, or any other reversible or non-cardiac cause
- EC 5 Structural heart disease as described below:
  - a. Left ventricular ejection fraction (LVEF) < 40% based on TTE within 6 months of enrollment

- b. Left atrial size > 50 mm based on TTE within 6 months of enrollment
  - c. An implanted pacemaker or ICD
  - d. Previous cardiac surgery, ventriculotomy, or atriotomy (excluding atriotomy for CABG (see EC 5, j)),
  - e. Previous cardiac valvular surgical or percutaneous procedure, or prosthetic valve
  - f. Interatrial baffle, closure device, patch, or PFO occluder
  - g. Presence of a left atrial appendage occlusion device
  - h. Coronary artery bypass graft (CABG) or PTCA procedure within the last 6 months
  - i. Unstable angina or ongoing myocardial ischemia
  - j. Myocardial infarction within the previous six (6) months
- EC 6 History of blood clotting or bleeding disease
- EC 7 ANY prior history of documented cerebral infarct, TIA or systemic embolism
- EC 8 Pregnant or lactating (current or anticipated during study follow up)
- EC 9 Current enrollment in any other study protocol in which testing or results from that study may interfere with the procedure or outcome measurements for this study
- EC 10 Any other condition that, in the judgment of the investigator, makes the patient a poor candidate for this procedure, the study or compliance with the protocol (includes vulnerable patient population, mental illness, addictive disease, terminal illness with a life expectancy of less than two years, or extensive travel away from the research center)

## **6.7 Subject Withdrawal**

Individual subjects may withdraw their consent to participate in the study at any time. Also, an Investigator may discontinue a subject's participation in the study at any time to protect the safety, rights, or welfare of the subjects.

Subjects missing follow-up visits will not be considered lost to follow-up until adequate attempts to contact the subject has been made by telephone, e-mail, and/or mailed letter.

## **7 CLINICAL STUDY TREATMENTS AND FOLLOW-UP VISITS**

### **7.1 Informed Consent**

It is the responsibility of the Investigator to give each subject full and adequate verbal and written information regarding all aspects of the study procedure, device, and associated risks. A signed, informed consent must be obtained from the subject before any study procedures not considered standard of care for an AF ablation are undertaken. The informed consent form must be signed by the subject and witnessed by the Investigator (or designee). The original signed consent is filed in the patient's study records with one copy placed in the patient's medical notes and one copy provided to the patient.

### **7.2 Patient Screening and Baseline**

The following information must be acquired to verify eligibility in the clinical study:

[figure not shown]
- Subject demographics
- Medical history review including:
  - All history of AF and other arrhythmias, including onset, duration, previous testing, etc.
  - Prior and current AAD treatments for AF
  - Medication history including AADs, pertinent cardiovascular drugs, and anticoagulation
  - DCCV history
  - Information supportive of determining a CHADS2 and CHA2DS2-VASc scores
- Review of all inclusion/exclusion criteria to confirm patient eligibility
- Physical exam
- Transthoracic echocardiogram (TTE) within the previous six (6) months to document:
  - Left atrial size
  - Left ventricular ejection fraction
  - Severity of any valvular heart disease
- Pregnancy test (if applicable)
- Routine standard of care laboratory and X-ray tests for pre-ablation work-up
- ECG or continuous ECG monitor tracing/report documenting AF

- Completion of a Patient Reported Outcome (AFQET)

### 7.3 Ablation Procedure

#### 7.3.1 Mapping and Ablation

The objective of this clinical study is to evaluate the safety and performance of the AcQMap System when mapping and imaging the left and right atria during persistent AF ablation. Therefore, the utilization of devices for 3D anatomic reconstruction, navigation and electrical mapping should be limited to the AcQMap System. Furthermore, RF ablation catheters utilized during the procedure should be limited to those compatible with the AcQMap System.

**Figure 1: Ablation Procedure Flow Diagram**

### **7.3.2 Procedure Data Collection**

Collection of data generated during the procedure should include:

- Medications and any change in health prior to the ablation
- Recording of 12 lead ECG at procedure start
- Recording of 12 lead ECG at procedure completion
- Total procedure time (from first venous access to study completion)
- Total fluoroscopy time and times to complete segments of the ablation procedure
- Ablation time to complete PVI (delineate RF vs Cryo)
- Ablation time for additional LA lesions (separate AF from AT ablations)
- Ablation times for right atrial ablations
- Recording of all DCCV used during the procedure
- EP recording of all atrial tachyarrhythmias noted during the procedure
- EP recording of conversion to sinus rhythm (either spontaneous or DCCV)
- EP recording demonstrating PV isolation of all treated veins
- Recording of any right atrial arrhythmias mapped and/or treated
- Recording of all AADs infused during the procedure
- Recording of any medications administered for anticoagulation reversal

## **7.4 Follow-Up Procedures**

### **7.4.1 Hospital Discharge**

The subjects should be monitored with telemetry prior to hospital discharge for the documentation of recurrence of atrial fibrillation or other atrial tachyarrhythmias.

The following evaluations should be completed prior to discharge:

- Physical exam (including neurological assessment)
- Medication history
- Evaluation of Adverse Events
- 12-lead electrocardiogram

Careful attention should be placed in the identification of potential cardiac effusions and post-procedure cardiac tamponade. Unexplained reduction in blood pressure, chest pain or

shortness of breath require a post-procedure TTE and further evaluation and management as indicated.

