#### **7.4.3 Visits at One, Three, Six, and Twelve Months**

The following evaluations will be performed during each clinic follow-up visit. Data will be recorded on the Follow-Up eCRFs.

- History and Physical exam (including neurological assessment)
- Medication history
- Adverse events assessment
- 12-lead electrocardiogram
- Echocardiogram (TTE at 12 months only, for comparison to baseline)
- AFEQT Questionnaire (completed prior to visit)
- 24-hour continuous monitor (3, 6, 9, and 12 months)
  - Since the 24-hour continuous monitor at 9-months does not coincide with a follow-up visit, the subject will be instructed how and when to wear the recording device. Once the recording is completed, the device will be returned to the study site and the results of the recording will be entered into an eCRF.

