### **12-Lead ECGs**

12-Lead ECGs will be performed in screening, prior to procedure (baseline), at the completion of procedure, prior to hospital discharge, and at one, three, six, and 12 months post-procedure. The number and percent of subjects with each ECG rhythm will be reported by time point.

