### **Physical Exam Findings**

Physical exams will be performed at screening (baseline), pre-procedure, discharge, and at the one, three, six, and 12 month follow up visits. A physical exam shift table will be constructed for each post-procedure time point in order to count the frequency of each shift for each body system. Shifts include normal/normal, normal/abnormal, abnormal/normal, and abnormal/abnormal.

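### The physical-exam shift tables take screening as baseline although a later pre-procedure exam is scheduled, so an abnormality that arises between the two exams and persists is shown as a post-procedure shift

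*Combined protocol and SAP*

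**What the plan says.** SAP 4.2.2, Physical Exam Findings, sets the timing: "Physical exams will be performed at screening (baseline), pre-procedure, discharge, and at the one, three, six, and 12 month follow up visits". It continues: "A physical exam shift table will be constructed for each post-procedure time point", with counts by body system. The categories are given as: "Shifts include normal/normal, normal/abnormal, abnormal/normal, and abnormal/abnormal". The shift sentence does not itself name the reference exam, but screening is the only exam labelled baseline. SAP 4.1.2 lists physical exam findings among the secondary safety measures.

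The schedule of events in the protocol (Tables 1 and 2) marks the history and physical exam under both Screening & Baseline and Procedure. Protocol 7.3.2 also collects "Medications and any change in health prior to the ablation".

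For the ECG, the same SAP section reads: "12-Lead ECGs will be performed in screening, prior to procedure (baseline), at the completion of procedure".

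On exam content, protocol 7.4.1 has "Physical exam (including neurological assessment" at discharge, and 7.4.3 has "History and Physical exam (including neurological assessment" at the clinic visits. Protocol 7.2 says only "Physical exam" for screening, and the 7.3.2 list names no neurological item.

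**The concern.** A shift table is read as change since treatment. That reading is safe only if the reference is the last state observed before treatment. Here a later pre-treatment exam is scheduled, and the table does not use it. Whatever changes between screening and the procedure is therefore attributed to the period after the procedure, even though the study has already recorded it beforehand.

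Other parts of the plan do not correct this inside the table. Protocol section 9 sends findings from before enrollment to the Medical History form and starts adverse-event counting once a subject is in the safety population, that is, at venous access. A finding that arises between those two points falls under neither rule. The change-in-health item in 7.3.2 would capture it, but nothing links that item to the shift table.

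At stake is the interpretation of one secondary safety display.

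**Working it through.** **The plan's own figure.** The only design calculation is the sample size (protocol 8.4, SAP 1.3): 125 subjects, half-width 3.89% at an observed 96.0%. With x = 120 and n = 125, the Clopper-Pearson limits are the 0.025 quantile of Beta(120, 6) = 0.9091 and the 0.975 quantile of Beta(121, 5) = 0.9869. Half-width = (0.9869 − 0.9091)/2 = 0.0389. The figure reproduces, and nothing in this point enters it.

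**Baselines side by side (SAP 4.2.2).**

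| Measure | Labelled baseline | Separate pre-procedure record scheduled? |
|---|---|---|
| Physical exam | Screening | Yes, and not used in the shift table |
| 12-lead ECG | Pre-procedure | Yes, and used as baseline |
| Vital signs | Screening | No |

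The physical exam is the only one of the three for which a later pre-treatment record is scheduled and passed over.

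**Tracing one body system** (screening, pre-procedure, post-procedure; N = normal, A = abnormal).

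| Pattern | Screening as baseline | Last exam before venous access as baseline |
|---|---|---|
| N, N, A | normal/abnormal | normal/abnormal |
| N, A, A | normal/abnormal | abnormal/abnormal |
| A, A, A | abnormal/abnormal | abnormal/abnormal |

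Of these, only the second pattern is misattributed. It needs a normal screening result, an abnormality arising before the procedure, and persistence to a post-procedure exam.

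**Scale, by assumption only.** The documents give no rate for the second pattern. If a fraction q of 125 subjects showed it, the count is 125 × q:
- 1%: 1.25
- 2%: 2.5
- 5%: 6.25
- 10%: 12.5

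If q is instead taken as the rate of any finding arising in the interval, these counts are ceilings, because some findings resolve or fall in a body system already abnormal at screening. The table is built on the treatment population, and 125 is taken here as its size.

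**Neurological content.** The assessment is named at discharge (protocol 7.4.1) and at 1, 3, 6 and 12 months (protocol 7.4.3, SAP 1.2). It is not named at screening (protocol 7.2, SAP 1.2) or in the procedure list (protocol 7.3.2). Every shift category needs a baseline state. SAP 2.3 prescribes complete-case analysis, and its exceptions (Holter rhythm and dates) do not cover the physical exam. A subject with no neurological baseline therefore contributes no neurological shift.

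**The case against.** The best defence is that the choice is declared in advance, matches vital signs, and affects a descriptive table in a study without hypothesis tests (SAP 2.1). The ECG records the rhythm being treated, so a different reference there need not be an inconsistency. The low stakes are real. The vital-signs parallel does not hold, because SAP 4.2.2 schedules no pre-procedure vital signs, so screening is the only pre-treatment reading. The ECG contrast does not by itself prove an error. It does show that the SAP uses the nearer record elsewhere, and no reason is given for departing from that here.

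Three stronger readings are tempting, and the documents support none of them.

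- **Pre-existing neurological deficits are counted as new.** This would require an unassessed baseline to be read as normal, which no section says. It is also not established that the baseline lacks neurology. Tables 1 and 2 use one exam row throughout, and SAP 1.2 calls the discharge exam simply a physical exam although protocol 7.4.1 includes neurology in it. The content is unspecified, not shown to be absent. A nervous-system row is itself an inference from the reference to body systems, since the table shells are not in the supplied text.
- **The primary result could move.** The primary endpoint rests on events adjudicated by the Clinical Events Committee, not on the shift table. Documented prior infarct, TIA or systemic embolism is excluded (EC 7), and medical history and pre-ablation changes are recorded. Nor is the discharge neurological exam the only check, because 7.4.1 separately requires an adverse-event evaluation.
- **The plan leaves the screening-to-procedure interval open.** No limit is visible, but the Screening column carries a footnote mark whose text is not visible in the supplied copy, so this cannot be concluded.

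**Conclusion.** The point holds in a limited form. With screening as the shift-table baseline, an abnormality that first appears between screening and the procedure and persists is tabulated as a normal/abnormal shift after the procedure. A finding already recorded at screening is not counted as new. This rests on reading the baseline label in SAP 4.2.2 as the shift-table reference, which is the only reading the text offers.

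The consequence is confined to a descriptive secondary safety table. Adverse-event tables classify by onset time and are unaffected, as are the primary proportion, its interval and the sample size. The number of subjects involved cannot be derived from the documents, and the counts shown above only translate assumed rates.

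The neurological gap is a matter of clarification. If no baseline assessment exists, the neurological shift cannot be assessed. It is not inflated.

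**What to change.** In SAP 4.2.2, Physical Exam Findings, state that baseline for the shift tables is the last physical exam before venous access: the pre-procedure exam, or the screening exam where the pre-procedure result is missing for that body system. This costs one SAP sentence and the matching derivation in the programs. Both exams are already scheduled, so no new data are needed.

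As a minor clarification, reconcile protocol 7.2, 7.3.2, 7.4.1 and 7.4.3 with SAP 1.2 on whether the pre-treatment exams include the neurological assessment. If they do, say so. If they do not, the SAP should state that neurological shifts are not assessable. Any change to the protocol wording is an amendment and needs ethics committee notification or approval under protocol 11.15.1. The SAP change does not depend on it and can go ahead alone.

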#### **7.4.2 Seven Day Phone Follow-Up**

Subjects should be contacted by phone at seven ( $7 \pm 3$ ) days following their discharge from the hospital. Information regarding their groin access sites and sense of any irregular heart rate should be obtained. The Study Coordinator should also review current medications, review the follow-up schedule, and answer any questions the subject might have. If any concerns arise that suggest adverse events, the subject may be asked to return to clinic for a thorough evaluation. Any visits prior to the one-month visit should be captured on the Unscheduled Visit eCRFs.

#### **7.4.3 Visits at One, Three, Six, and Twelve Months**

The following evaluations will be performed during each clinic follow-up visit. Data will be recorded on the Follow-Up eCRFs.

- History and Physical exam (including neurological assessment)
- Medication history
- Adverse events assessment
- 12-lead electrocardiogram
- Echocardiogram (TTE at 12 months only, for comparison to baseline)
- AFEQT Questionnaire (completed prior to visit)
- 24-hour continuous monitor (3, 6, 9, and 12 months)
  - Since the 24-hour continuous monitor at 9-months does not coincide with a follow-up visit, the subject will be instructed how and when to wear the recording device. Once the recording is completed, the device will be returned to the study site and the results of the recording will be entered into an eCRF.

#### **7.4.4 Unscheduled Visits**

Any visit outside of the scheduled follow-up visit windows will be considered an unscheduled visit. All pertinent data will be recorded on the Follow-up Visit eCRF.

### **7.5 Recurrence of Atrial Fibrillation/Atrial Flutter/Atrial Tachycardia (AF/AFL/AT)**

#### Arrhythmia Recurrence during the Blanking Period

Occurrences of symptomatic atrial fibrillation or other (tachyarrhythmias) during the first 90 days post-ablation (blanking period) may be transient in nature and not associated with the

long-term effectiveness of the ablation treatment. However, prolonged AF should be treated as soon as possible to maintain sinus rhythm during the remodeling period. Treatment should follow the Investigator's standard of care for AF recurrence, which may include a DCCV and/or AAD administration. Repeat ablations may be considered during the blanking period; however, they are discouraged.

#### Arrhythmia Recurrence beyond the Blanking Period

Development of AF/AFL/AT beyond the blanking period should first be documented with an ECG or a 24-hour continuous ECG monitor. Recurrence of an arrhythmia will be recorded on the eCRF as part of the continued management process of the subject in follow-up. These will be documented at unscheduled or routine (three-, six- and twelve-month) follow up visits.

Treatment should follow the Investigator's standard of care and may include DCCV, AAD administration or repeat ablation (retreatment procedure). Use of a DCCV is recommended prior to an ablation as many of these arrhythmias may be self-limited. One retreatment is allowed and may only occur in the time range from day 91 through day 270 post-ablation.

In a retreatment procedure, the AcQMap System should be used following the same protocol as the index procedure. Documentation of the retreatment will be on the procedure retreatment eCRF form. Follow-up visits will restart using the same schedule as with the index procedure (7-day call, 1, 3, 6 months); however, the study completion date (12 months from the index procedure) will not change.

[figure not shown]
**Hospital admissions and clinic visits to treat these arrhythmias (cardioversion, in-patient medication change and ablation) will not constitute an SAE but will be reported as an additional intervention to the management of the persistent AF.** In the event the subject suffers an untoward or unanticipated complication as a result of the arrhythmia (i.e. thrombotic event, pulmonary edema etc.), an adverse event reporting will occur and be adjudicated by the Clinical Events Committee in accordance with the CEC Charter.

Screening, procedure and follow-up visits are outlined in Table 2 and a flow diagram of visits is pictured in Figure 10.

**Table 2: Schedule of Events**

	Screening  & Baseline	Procedure	Discharge	7 Days (± 3 days) Phone Contact	1-month (± 7 days)	3-month (± 14 days)	6-month (± 30 days)	9-month (± 30 days)	12-month (± 30 days)
CIP Informed Consent	X								
Medical History	X								
History & Physical Exam	X	X	X		X	X	X		X
Medications	X	X	X		X	X	X		X
Transthoracic Echo (TTE)	X (within 6 months)								X
Trans Esophageal Echo (TEE)		X (within 72 hours)							
Adverse Events		X	X	X	X	X	X		X
12-lead ECG	X	X	X		X	X	X		X
Labs	X								
HCG (female patients)	X								

	Screening  & Baseline	Procedure	Discharge	7 Days (± 3 days) Phone Contact	1-month (± 7 days)	3-month (± 14 days)	6-month (± 30 days)	9-month (± 30 days)	12-month (± 30 days)
Patient Reported Outcome Measures (AFEQT)	X				X	X	X		X
24-hour Continuous ECG Monitor Recording							X	X	X

1. Index Ablation and no additional procedures
2. Index Ablation and only DCCV or AAD through Month 3
3. DCCV, AAD, repeat ablation beyond blanking period, through Month 9

**Figure 2: Flow Diagram of Follow-Up and Retreatment Procedures**

## 8 STATISTICAL METHODS

### 8.1 Analysis Population

The following analysis populations will be defined for the study:

**Safety Population** – The safety population will include all enrolled subjects who have the venous access portion of the ablation procedure initiated.

**Treatment Population** – The treatment population will include all enrolled subjects who complete a procedure up to the point the AcQMap catheter is deployed in the left atrium.

### 8.2 Statistical Analysis for Primary Safety Outcome Measure

The primary outcome measure for the study is the primary safety objective, defined as the proportion of subjects who are free from device/procedure related Major Adverse Events (MAEs), as adjudicated by the CEC, that occur within the first twenty-four (24) hours post-procedure. Subjects who remain free from such device/procedure related MAEs will be considered a success with respect to the primary safety objective, and subjects who experience at least one such MAE will be considered a primary safety failure. MAEs that occur during the first 24 hours will be reported and adjudicated by the CEC for any probable relationship to the device and/or procedure.

### 8.3 Statistical Analysis for Secondary Outcome Measures

Descriptive statistics will be applied to the secondary outcome measures

### 8.4 Study Size Justification

The total sample size for the combined studies was selected based on the primary safety objective of the study. In order to estimate the primary safety objective within a margin of error of 3.89% (i.e., this is the 95% confidence interval half-width), assuming the observed proportion of subjects who are free from device/procedure related Major Adverse Events (MAEs) that occur within the first 24 hours post-procedure is 96.0%, a total of 125 subjects is required. These calculations assume the data are from a binomial distribution and that the confidence interval will be computed using the Clopper-Pearson exact approach.

## 9 ADVERSE EVENTS

For the purpose of this protocol, an adverse event is any untoward medical occurrence, unintended disease or injury, or any untoward clinical signs in subjects whether or not related to the AcQMap System, and includes events related to the procedures involved

in the clinical investigation plan. Any adverse event (AE) that occurs in a subject once they are considered a “safety” population is considered an AE. Any medical conditions, problems, signs, symptoms, and findings occurring prior to enrollment are to be reported as pre-existing conditions on the Medical History eCRF.

